10.3.1.2 Serious Adverse Events

A serious adverse event (SAE) is defined as an adverse event that meets any of the following criteria:

1. Results in death.
2. Is life threatening: that is, poses an immediate risk of death as the event occurred.
 - a. This serious criterion applies if the study subject, in the view of the Site Investigator or Sponsor, is at immediate risk of death from the AE as it occurs. It does not apply if an AE hypothetically might have caused death if it were more severe.
3. Requires inpatient hospitalization or prolongation of existing hospitalization.
 - a. Hospitalization for an elective procedure (including elective PEG tube/g-tube/feeding tube placement) or a routinely scheduled treatment is not an SAE by this criterion because an elective or scheduled "procedure" or a "treatment" is not an untoward medical occurrence.
4. Results in persistent or significant disability or incapacity.
 - a. This serious criterion applies if the "disability" caused by the reported AE results in a substantial disruption of the subject's ability to carry out normal life functions.
5. Results in congenital anomaly or birth defect in the offspring of the subject (whether the subject is male or female).
6. Necessitates medical or surgical intervention to preclude permanent impairment of a body function or permanent damage to a body structure.
7. Important medical events that may not result in death, are not life-threatening, or do not require hospitalization may also be considered SAEs when, based upon appropriate medical judgment, may jeopardize the subject and may require medical or surgical intervention to prevent one of the outcomes listed in this definition. Examples of such medical events include blood dyscrasias or convulsions that do not result in inpatient hospitalization, or the development of drug dependency or drug abuse.

An inpatient hospital admission in the absence of a precipitating, treatment-emergent, clinical adverse event may meet criteria for "seriousness" but is not an *adverse* experience, and will therefore, not be considered an SAE. An example of this would include a social admission (subject admitted for other reasons than medical, e.g., lives far from the hospital, has no place to sleep).

A serious, suspected adverse drug reaction is an SAE that, in the opinion of the Site Investigator or Sponsor, suggests a reasonable possibility that the investigational product caused the event.

The Site Investigator is responsible for classifying adverse events as serious or non-serious.

10.3.1.3 Assessment and Recording of Adverse Events

Assessment of Adverse Events

At each visit (including telephone interviews), the subject will be asked "Have you had any problems or symptoms since your last visit?" in order to determine the occurrence of adverse events. If the subject reports an adverse event, the Investigator will determine:

1. Type of event
2. Date of onset and resolution (duration)
3. Severity (mild, moderate, severe)
4. Seriousness (does the event meet the above definition for an SAE)
5. Causality, relation to investigational product and disease
6. Action taken regarding investigational product
7. Outcome

Relatedness of Adverse Event to Investigational Product

The relationship of the AE to the investigational product should be specified by the Site Investigator, using the following definitions:

1. Not Related: Concomitant illness, accident or event with no reasonable association with treatment.
2. Unlikely: The reaction has little or no temporal sequence from administration of the investigational product, and/or a more likely alternative etiology exists.
3. Possibly Related: The reaction follows a reasonably temporal sequence from administration of the investigational product and follows a known response pattern to the suspected investigational product; the reaction could have been produced by the investigational product or could have been produced by the subject's clinical state or by other modes of therapy administered to the subject. (suspected ADR)
4. Probably Related: The reaction follows a reasonably temporal sequence from administration of investigational product; is confirmed by discontinuation of the investigational product or by re-challenge; and cannot be reasonably explained by the known characteristics of the subject's clinical state. (suspected ADR)
5. Definitely Related: The reaction follows a reasonable temporal sequence from administration of investigational product; that follows a known or expected response pattern to the investigational product; and that is confirmed by improvement on stopping or reducing the dosage of the investigational product, and reappearance of the reaction on repeated exposure. (suspected ADR)

Recording of Adverse Events

All clinical adverse events are recorded in the Adverse Event (AE) Log in the subject's study binder. The site should fill out the AE Log and enter the AE information into the online Adverse Event Reporting System within 5 working days of the site learning of a new AE or receiving an update on an existing AE.

Please Note: Serious Adverse Events (SAEs) must be reported to the NeuroNEXT Data Coordinating Center within 24 hours of the site learning of the SAE.

Entries on the AE Log (and into the online Adverse Event Reporting System) will include the following: name and severity of the event, the date of onset, the date of resolution, relationship to investigational product, action taken, and primary outcome of event.

Adverse Events and Serious Adverse Events - Reportable Events

The following are considered reportable events and must be reported to the PI within 24 hours of the site being notified of the event.

- All events that meet the above criteria for Serious Adverse Events (SAEs)

All occurrences of Serious Adverse Events (SAEs) must be reported within 24 hours of discovery of the event. All other Adverse Events (AEs) must be reported within *insert timeline for reporting* (of discovery of the event).

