6.3.8 Clinical Assessments

- Hoehn & Yahr
 - Collected to measure disease severity as well as progression throughout study
- Orthostatics
 - Collected to measure if participants are having worsening orthostatic hypotension.
 - If orthostatic hypotension is present, this assessment will NOT be able to determine if it is secondary to the study medication or autonomic failure that occurs in PD.
- Physical examination
 - This will be a simple physical exam to measure the general health of the participant independent of their PD
- MDS UPDRS Part 3
 - This portion of the MDS-UPDRS specifically measures motor function. This will only be collected when subjects are in the practically defined "off-period" meaning that they have not taken their PD medications within 6 hours of the assessment
- MDS-UPDRS Part 4
 - This portion of the MDS-UPDRS will use historical and objective information to assess the motor complications of dyskinesia and motor fluctuations including off-state dystonias
- Vital signs/Height & Weight

FAST TZ-PD

Version 2.0

Version date: 11/12/2019

- Participants will have their heart rate, respiratory rate, blood pressure, and core body temperatures measured as well as their height and weight
- Neurological Exam

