9 STATISTICAL CONSIDERATIONS

9.1 Outcomes

9.1.1 Primary Outcome (including definition)

The primary outcome measure will be the safety and tolerability of TZ in the select patient population. This will be assessed by comparing the number of participants in each group that experience drug-related adverse drug events as well as assessing the rate of drop out in each group.

To assess the mean change in systolic and diastolic blood pressures at 6 weeks and 12 weeks between the active and placebo groups.

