9.4 Data Analyses

The following outcome measures will be analyzed under an intention-to-treat protocol. All randomized individuals will be included regardless of their final treatment status.

- Primary Outcome
 - Rate of drop out between groups
 - Chi-square
 - Rate of adverse events between groups
 - Chi-square
- Secondary outcomes
 - Prevalence of orthostatic hypotension between placebo and active group
 - Chi-square
 - Prevalence of falls between placebo and active group
 - Chi-square
 - Differences in overall compliance between placebo and active group
 - Linear mixed effect models that includes compliance at each study visit for each participant
- Exploratory outcomes
 - Difference in ATP levels in red blood cells and brain within subjects before and after taking study drug on day 1
 - Paired samples t-test
 - Difference in ATP levels in red blood cells and brain within subjects at 6 and 12 weeks compared to baseline reading

- Paired samples t-test
- Difference in ATP levels in red blood cells and brain between groups at 6 weeks and 12 weeks
 - Independent samples t-test
- Slope of change over 12 weeks of the MDS-UPDRS Part 1
 - LMER
- Slope of change over 12 weeks of the MDS-UPDRS Part 2
 - LMER
- Slope of change over 12 weeks of the MDS-UPDRS Part 3
 - LMER
- Slope of change over 12 weeks of the MDS-UPDRS Part 4
 - LMER
- Absolute change over 12 weeks of the MDS-UPDRS Parts 1, 2, 3, 4, and TMS
 - Independent samples t-tests
- Slope of change over 12 weeks of MDS-UPDRS TMS (direct comparison for efficacy)
 - LMER
- Slope of change over 12 weeks of the Hoehn & Yahr Score
 - LMER
- Slope of change over 12 weeks of all cognitive assessments between placebo and active group
 - LMER
- Slope of change over 12 weeks of sleep assessments between placebo and active group
 - LMER
- Slope of change over 12 weeks of behavioral assessments between placebo and active group
 - LMER

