10.3 Adverse Experience Reporting

The adverse event (AE) definitions and reporting procedures provided in this protocol comply with all applicable United States Food and Drug Administration (FDA) regulations and International Conference on Harmonization (ICH) guidelines. The PI will carefully monitor each subject throughout the study for possible adverse events. All AEs will be documented on CRFs designed specifically for this purpose. It is important to report all AEs, especially those that result in permanent discontinuation of the investigational product being studied, whether serious or non-serious.

Receipt will be kept in the investigator's study file.

An adverse event is defined as: "an unfavorable and unintended sign, symptom, or disease associated with a subject's participation in this research trial."

Serious adverse events include those events that: "result in death; are life-threatening; require inpatient hospitalization or prolongation of existing hospitalization; create persistent or significant disability/incapacity, or a congenital anomaly/birth defects."

Unexpected adverse event is defined as any adverse experience...the specificity or severity of which is not consistent with the risks described in the protocol.

Expected adverse events are those that are known to be associated with or have the potential to arise as a consequence of participation in the study.

On-line Adverse Event Reporting System

Serious adverse events: The site investigator determines causality (definitely not related, probably not related, possibly related, probably related, definitely related) of the adverse event. The PI will prepare a Medwatch safety report for submission to the FDA.

Non-serious adverse events: Non-serious adverse events that are reported to or observed by the investigator or a member of his research team will be submitted to the PI within 24 hours.

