10.3.1 Definitions of Adverse Events, Suspected Adverse Drug Reactions & Serious Adverse Events

10.3.1.1 Adverse Event and Suspected Adverse Drug Reactions

An adverse event (AE) is any unfavorable and unintended sign (including a clinically significant abnormal laboratory finding, for example), symptom, or disease temporally associated with a study, use of a drug product or device whether or not considered related to the drug product or device.

Adverse drug reactions (ADR) are all noxious and unintended responses to a medicinal product related to any dose. The phrase "responses to a medicinal product" means that a causal relationship between a medicinal product and an adverse event is at least a reasonable possibility, i.e., the relationship cannot be ruled out. Therefore, a subset of AEs can be classified as suspected ADRs, if there is a causal relationship to the medicinal product.

Examples of adverse events include: new conditions, worsening of pre-existing conditions, clinically significant abnormal physical examination signs (i.e. skin rash, peripheral edema, etc), or clinically significant abnormal test results (i.e. lab values or vital signs), with the exception of outcome measure results, which are not being recorded as adverse events in this trial (they are being collected, but analyzed separately). Stable chronic conditions (i.e., diabetes, arthritis) that are present prior to the start of the study and do not worsen during the

FAST TZ-PD

Version 2.0

Version date: 11/12/2019

trial are NOT considered adverse events. Chronic conditions that occur more frequently (for intermittent conditions) or with greater severity, would be considered as worsened and therefore would be recorded as adverse events.

Adverse events are generally detected in two ways:

Clinical → symptoms reported by the subject or signs detected on examination.

Ancillary Tests → abnormalities of vital signs, laboratory tests, and other diagnostic procedures (other than the outcome measures: the results of which are not being captured as AEs).

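### The known-pattern condition in Possibly Related contradicts the protocol's own definition of a suspected drug reaction and leaves some plausible new reactions without a causality category

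*Combined protocol and SAP*

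**What the plan says.** Section 9.1.1 assesses safety by "comparing the number of participants in each group that experience drug-related adverse drug events", together with drop-out. Section 9.4 lists the primary event analysis as "Rate of adverse events between groups", by chi-square, with no relatedness condition. No section states which causality levels make an event drug-related.

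Section 10.3.1.3 defines five levels for adverse events and tags the upper three as suspected ADRs:

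- *Not Related*: "Concomitant illness, accident or event with no reasonable association with treatment".
- *Unlikely*: "The reaction has little or no temporal sequence from administration of the investigational product, and/or a more likely alternative etiology exists".
- *Possibly Related*: reasonable timing "and follows a known response pattern to the suspected investigational product", where the drug, the clinical state or another treatment could be the cause.
- *Probably Related*: reasonable timing, confirmation by stopping or re-challenge, and no reasonable explanation from the clinical state. There is no known-pattern condition.
- *Definitely Related*: reasonable timing, a known or expected pattern, improvement on stopping or reducing the dose, and recurrence on re-exposure.

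Section 10.3.1.1 is broader. It counts as a drug response any case in which "a causal relationship between a medicinal product and an adverse event is at least a reasonable possibility, i.e., the relationship cannot be ruled out", and it goes on to define a reaction that is both unexpected and suspected. For serious events, section 10.3 lists a scale of "definitely not related, probably not related, possibly related, probably related, definitely related" and defines none of its levels.

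**The concern.** If the primary safety measure counts drug-related events, the causality scale is its measuring instrument. An instrument that admits a suspected reaction at its lowest level only when the pattern is already known works against the purpose of a safety trial in a new population, where unfamiliar reactions are among the things to be found. The investigator must still record a relationship for every event. Where no definition fits, the grade is improvised, and nothing says whether the event counts.

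**Working it through.** The plan gives no calculated figure on this point (section 9.2 bases the sample size on funding and resources), so there is none to reproduce. The check is one of logic.

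**Step 1. Event considered.** Timing is reasonable, an association with treatment is reasonable, and no alternative cause is more likely. *Not Related* fails because there is a reasonable association. *Unlikely* fails because the timing fits and no alternative is more likely. Only the upper three levels remain.

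**Step 2. Conditions that vary.** Pattern known or new (2); clinical state could explain the event or not (2); confirmation by neither, one, or both of stopping and re-exposure (3). This gives 2 × 2 × 3 = 12 combinations.

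| Pattern | Clinical state could explain | Confirmation | Levels that fit |
|---|---|---|---|
| New | No | None | None |
| New | No | One | Probably |
| New | No | Both | Probably |
| New | Yes | None | None |
| New | Yes | One | None |
| New | Yes | Both | None |
| Known | No | None | Possibly |
| Known | No | One | Possibly, Probably |
| Known | No | Both | Possibly, Probably, Definitely |
| Known | Yes | None | Possibly |
| Known | Yes | One | Possibly |
| Known | Yes | Both | Possibly, Definitely |

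**Step 3. Count.** New pattern: 2 of 6 fit a level and 4 of 6 do not. Known pattern: 6 of 6 fit. Overall, 8 of 12 fit. Without the known-pattern condition in *Possibly Related*, 6 of 6 new-pattern combinations and 12 of 12 overall fit. These are counts of logical cases, not frequencies; the documents give no basis for how often each would occur.

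**Step 4. Against the protocol's own definition.** In all four unplaced cases the link cannot be ruled out, so section 10.3.1.1 makes the event a suspected reaction. Section 10.3.1.3 gives it no level.

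**Step 5. Weight of one participant.** With 10 per arm, 1/10 = 10 percentage points. The documents give no event rates, significance level or continuity correction, so the counts below are assumed. The uncorrected statistic is N(ad − bc)² divided by the product of the four margins. For 6 v 1 it is 20 × 50² / (10 × 10 × 7 × 13) = 5.49. For 5 v 1 it is 20 × 40² / (10 × 10 × 6 × 14) = 3.81.

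| Active v placebo | Chi-square p | With Yates correction | Fisher exact |
|---|---|---|---|
| 6 v 1 | 0.019 | 0.061 | 0.057 |
| 5 v 1 | 0.051 | 0.143 | 0.141 |
| 7 v 2 | 0.025 | 0.072 | 0.070 |
| 6 v 2 | 0.068 | 0.171 | 0.170 |
| 5 v 0 | 0.010 | 0.039 | 0.033 |
| 4 v 0 | 0.025 | 0.094 | 0.087 |

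At an assumed 0.05 level, dropping one active-arm participant changes the uncorrected reading in the first two pairs but not the third. With Yates or Fisher it changes only the third.

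**The case against.** The strongest answer is section 9.4. If its analysis governs, every adverse event counts whatever its grade, and the gap does not touch the primary test; drop-out needs no causality grade either. That stands, and it makes the effect conditional. It does not remove the conflict, because section 9.1.1 specifies drug-related events.

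Information on stopping may also be common. Section 6.2.3 has participants with adverse effects stop study drug at once, section 7 limits this to intolerable effects, and section 9.3 follows ongoing events to resolution. Sections 6.2.3 and 7 need to be reconciled. The more often drug is stopped, the more new reactions could reach *Probably Related*, but not those that the clinical state could explain. Finally, a misgraded event changes the count only if that participant has no other counted event.

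A reader might infer more than the documents support:

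- *That no new reaction can be graded.* *Probably Related* admits those confirmed by stopping or re-challenge and not explained by the clinical state.
- *That only the 12 events listed in section 7 are known patterns.* No section makes that link. Section 10.3.1.1 judges expectedness against the investigator's brochure, the package insert or the protocol.
- *That falls drop out of view.* Section 4.4 names them among examples of side effects, and section 9.4 compares them between arms without attribution.
- *That orthostatic hypotension cannot be graded.* It is a listed effect, and *Possibly Related* allows for the clinical state as a cause. The remark in section 6.3.8 that "this assessment will NOT be able to determine if it is secondary to the study medication or autonomic failure that occurs in PD" concerns that measurement and does not bar an overall judgement by the investigator.
- *That an unreachable Definitely Related lowers the count.* All three upper levels carry the same tag, so a yes/no count does not depend on which applies.
- *That two rules mix in the primary count.* The scales in 10.3 and 10.3.1.3 share their top three labels, and the definitions in 10.3.1.3 cover serious events too. What remains is different lower labels, and no definitions in 10.3.
- *That events might be graded unblinded.* Section 4.5.4 withholds the codes from investigators until the study is complete.

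**Conclusion.** The conflict between 10.3.1.3 and 10.3.1.1 is real and should be corrected. A plausible new reaction that is unconfirmed, or that Parkinson's disease or another feature of the clinical state could also explain, has no level, although the protocol elsewhere calls it a suspected reaction. The conclusion rests on reading the definitions as written and on taking the suspected-ADR tags as the implied cut-off for drug-related. How many participants would be affected cannot be estimated from the documents. Any effect on the primary count arises only if 9.1.1, rather than 9.4, fixes what is counted.

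**What to change.** 1. In 10.3.1.3, delete the known-pattern condition from *Possibly Related*. Leave the rest of that definition, and the whole of *Unlikely*, unchanged, so that an event with a more likely alternative cause is still graded *Unlikely* and the two levels do not overlap further.
2. In 9.1.1, state that drug-related means possibly, probably or definitely related on this scale.
3. Align 9.4 with 9.1.1, for example by reporting participants with any adverse event and participants with a drug-related adverse event.
4. In 10.3, use the defined scale of 10.3.1.3 for serious events.

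The cost is rewording in four sections and matching labels on the adverse event log. Somewhat more events will be graded possibly related, in both arms.

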11 HUMAN SUBJECTS

Documented approval from the IRB will be obtained for all participating centers prior to clinical trial start, according local laws, regulations and organization. When necessary, an extension, amendment or renewal of the IRB approval must be obtained.

Evidence of training in responsible conduct of research shall be on file for each PI and co-investigator.

11.1 Institutional Review Board (IRB) Review and Informed Consent

This protocol and the informed consent document (Appendix A) and any subsequent modifications will be reviewed and approved by the University of Iowa IRB responsible for oversight of the study. A signed consent form, approved by the IRB, will be obtained from the subject. For subjects who cannot provide consent for themselves, such as those below the legal age, a parent, legal guardian, or person with power of attorney, must sign the consent form; additionally, the subject's assent must also be obtained if he or she is able to understand the nature, significance, and risks associated with the study. The consent form will describe the purpose of the study, the procedures to be followed, and the risks and benefits of participation. A copy of the consent form will be given to the subject, parent, or legal guardian, and this fact will be documented in the subject's record.

